10.4. Premature end of the study

This visit is identical to the final visit.

11. PREMATURE END OF THE STUDY/ END OF THE STUDY

11.1. Withdrawal criteria

Any person who in the course of the trial:

- decides to withdraw the consent for any reason
- does not present to the study visits
- does not comply with the treatment
- develops any of the conditions specified in the original exclusion criteria
- contracts a serious illness that does not allow the study continuation

DERMING S.r.l., Clinical Research and Bioengineering Institute [name]

[contact] - www.derming.com

Test code: E0122

- other reason of the patient to quit.

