5.4 Exclusion criteria

- Pregnancy;
- lactation;
- smokers;
- alcohol or drug abusers;
- subjects not in menopause who do not use adequate contraceptive precautions in order to avoid pregnancies during the study;
- Body Mass Index (BMI) variation (± 1) during the study period;
- performing non-surgical skin aesthetic procedures for hands in the 6 months prior to the study start;
- aesthetic surgical procedure for the hands in the past;
- change in the normal habits regarding food, physical activity, cosmetic products and cleansing for the hands during the month preceding the test;
- sensitivity to the test product or its ingredients (to be assessed by the investigator during the baseline visit);
- subjects whose insufficient adhesion to the study protocol is foreseeable;
- participation in a similar study currently or during the previous 6 months.)
- presence of cutaneous disease on the tested area, as lesions, scars, malformations;
 - clinical and significant skin condition on the test area (e.g. active eczema, psoriasis, scleroderma, local infections).

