9.2.3. AEs/Incidents reporting procedure

All incidents and adverse events (AEs) or adverse device effect (ADE) regardless the seriousness must be reported in the source file (if applicable) and in the "Adverse event form" (see "CRF" enclosed in Appendices section). Investigators are responsible for documenting adverse events in the eCRF section created for this purpose.

Moreover, the investigator must determine:

- if the event is serious or not
- if the event is related or not related to the study treatment.

Any adverse event, related or not related to the study treatment, must be documented and will be followed until completed resolution (see paragraph 8.2.3.).

Then, the investigator will decide to:

- interrupt definitively the study treatment
- continue the study as protocol directed
- interrupt temporary the study treatment
- end the study

In case a subject's withdraws from the trial, the form "End of Study" should be filled in and the reasons for discontinuation recorded. The withdrawal subject should be encouraged to attend the final visit for the last study assessment.

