9.2.3. Adverse event follow up

All SAEs should be followed-up by the Investigator in order to elucidate as completely and practically as possible their nature and/or causality until resolution of all queries, clinical recovery is complete, laboratory results have returned to normal, stable condition is reached or the subject is lost to followup.

If the study product causes an adverse event, the Investigator could withdraw the subject from the study. During the final visit the Investigator will determine whether the adverse event is ongoing or

DERMING S.r.l., Clinical Research and Bioengineering Institute [name]

[contact] - www.derming.com

Test code: E0122

resolved. In any case it must be followed up to complete resolution.

The Investigator could decide to momentarily suspend the treatment and then to reintroduce it, only if the subject agrees and if the adverse event has been classified “mild/moderate” and its relationship to the study product results unlikely/possible.

All further follow up visits necessary to monitor the adverse event, will be recorded in the adverse event form.

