12.2. Population description

This sample includes all subjects that completed the study according to the protocol.

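### Section 11.1 makes a local complication that matches an exclusion condition a ground for withdrawal, and section 12.2 then leaves withdrawn subjects out of the month-4 performance result

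*Combined protocol and SAP*

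**What the plan says.** Section 11.1 (Withdrawal criteria) is a list that applies to any person in the course of the trial. One entry is that the person "develops any of the conditions specified in the original exclusion criteria". Among the conditions in section 5.4 is "presence of cutaneous disease on the tested area, as lesions, scars, malformations", and another entry there covers significant skin conditions on the test area, with local infection as an example.

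The adverse event text is more flexible. Under AEs/Incidents reporting procedure (9.2.3), one of the investigator's options is to "interrupt definitively the study treatment", listed separately from ending the study. On subjects who do withdraw it adds: "The withdrawal subject should be encouraged to attend the final visit for the last study assessment". Under Adverse event follow up (also numbered 9.2.3) it says: "If the study product causes an adverse event, the Investigator could withdraw the subject from the study". It also provides for a pause: "The Investigator could decide to momentarily suspend the treatment and then to reintroduce it, only if the subject agrees", under further conditions on severity and causality. On the event itself it says: "In any case it must be followed up to complete resolution".

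Section 10.4 gives the premature-end visit the same content as the final visit but no date.

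Section 12.2 defines the only sample in the analysis plan: "This sample includes all subjects that completed the study according to the protocol". Section 1 names performance and tolerance together as the primary endpoint.

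**The concern.** Whether a treated subject counts in the month-4 performance result can depend on how that subject's skin reacted to treatment. A subject who develops a lesion or infection at the injection site meets a withdrawal criterion, and a withdrawn subject has not completed according to the protocol. The study has a single arm, so the problem is not imbalance between groups. The problem is that the reported performance may describe only subjects without such a complication.

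Withdrawal is not needed for protection either. Before T1, withholding the second injection protects the subject. After T1 no injection remains to be withheld.

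**Working it through.** No power or error-rate calculation applies. The check is a reading of the sections against each other, plus a little arithmetic.

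**1. Can a condition caused by the injection trigger 11.1?** Yes. Lesions, scars and local infections on the test area are in section 5.4 and are plausible after injecting there. The list is also meant to operate after enrolment, since one of its entries is a BMI change of ±1 during the study. The ordinary expected reactions in section 9.1 (swelling, pain, erythema, bruise) are not captured as such. Product sensitivity is a weak trigger, because 5.4 says it is assessed at the baseline visit.

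**2. Does 11.1 mean leaving the study or only stopping injections?** Its setting points to leaving. Section 11 is headed as the end of the study, 11.2 uses a study termination form, and 11.3 speaks of volunteers who stop the trial. The neighbouring entry on serious illness is limited to illness that prevents continuation. The exclusion-condition entry has no such limit.

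**3. Set against the adverse event sections:**

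| Situation | Section 11.1 | Sections 9.2.3 |
|---|---|---|
| Local infection after the first injection | Withdrawal criterion, no qualification | Investigator may stop, pause or continue treatment, or end the study |
| Product-caused event | Withdrawal criterion if it matches an exclusion condition | Withdrawal is optional |

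Nothing says which text governs, so two investigators could handle the same case differently.

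**4. What happens in the analysis?** Sections 12.1 and 12.3 to 12.5 deal with clinical and instrumental data and change from baseline. The only sample is that of 12.2. A withdrawn subject is outside it on the plain reading, even if T2 is attended as encouraged. A subject who skips the second injection but stays in the study has probably not completed according to the protocol either, so aligning 11.1 alone would not be enough.

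**5. When does it matter?** T1 is at month 1 and T2 at month 4, so the last interval is 4 − 1 = 3 months, with 0 scheduled visits in between. If the condition is found at T1 or at an unscheduled contact before T2, the month-4 assessment is not secured. If it is first found at T2, the assessment is not lost.

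**6. The plan's own numbers.** Section 5.2 enrols 55 to obtain at least 50 evaluable cases. The allowance is 55 − 50 = 5, or 5/55 = 9.1%, and 50/(1 − 5/55) = 55 reproduces the stated figure. This covers losses of every kind and is not an estimate for this route.

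**7. Illustration only.** Suppose k of the 55 injected subjects are left out, all 55 would have had T2 data, and those left out do worse by D standard deviations. The completer mean is then too favourable by (k/55) × D. The documents give neither k nor D; the values below are assumptions.

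| k | D = 0.5 | D = 2 |
|---|---|---|
| 0 | 0 | 0 |
| 1 | 0.009 SD | 0.036 SD |
| 3 | 0.027 SD | 0.109 SD |
| 5 | 0.045 SD | 0.182 SD |

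**The case against.** The strongest reply is that the protocol already handles complications. Section 11.1 is an incomplete sentence that never says a subject must be withdrawn. It can be read as a list of grounds, with the more specific adverse event text governing complications and leaving withdrawal to the investigator. Withdrawn subjects are encouraged to attend the final visit, which is T2, and 10.4 offers the same assessments at premature end. A subject with a known event is followed to resolution and may have more contact than others. Section 3 reports no injection site reactions in preceding trials, so the group may be empty.

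Much of this stands. Mandatory withdrawal is not established, data collection is partly secured, and the affected group is narrow. But encouragement is not a planned assessment, the premature-end visit has no date, and none of these provisions returns the subject to the 12.2 sample.

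A reader might infer that the tolerance result is confined to completers, or that adverse events in withdrawn subjects are lost. The documents do not support this. Section 12 never mentions tolerance. Section 9.1 covers any adverse event during the study without a completer restriction, and 9.2.3 requires all events to be documented and followed. What can be said is that no denominator for tolerance is named.

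A reader might also infer that antihistamines or corticosteroids given for a reaction (section 5.4.2) would trigger withdrawal. That is only a possible reading, and the point does not rest on it.

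Finally, the completer-only sample would be a weakness whatever 11.1 said, since it also drops missed visits and non-compliance. That is correct. What 11.1 adds is a route into that loss that depends on the subject's reaction to treatment.

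**Conclusion.** The point holds for the month-4 performance result. Followed as written, 11.1 and 12.2 together allow a subject to drop out of it because of a local complication, and 11.1 is not aligned with the adverse event text. For tolerance, the finding is limited to the missing denominator.

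The size cannot be derived from the documents. With no such subject the effect is zero. Under the assumptions shown, with up to 5 subjects left out, the shift in the mean stays below 0.2 SD. The conclusion rests on reading 11.1 as leaving the study and 12.2 as excluding withdrawn subjects; both are the plain reading, though not the only one. Severity is minor to moderate, and the change is worth making because it is cheap.

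**What to change.** - **Section 11.1:** state that developing an exclusion condition stops or delays the second injection under the two 9.2.3 sections, and that neither before nor after T1 is it by itself a reason to leave the study. Pregnancy keeps its own rule in 9.2.4.
- **T2 visit:** injected subjects who still consent keep the planned T2 visit. For safety, the investigator may omit a contact measurement (pinch profilometry, torsiometry) on diseased skin. Add to 10.4 that a premature-end visit does not replace T2 for these subjects.
- **Section 12.2:** analyse performance in all injected subjects with T2 data, and report adverse events over all injected subjects, whether or not they reach T2. Flag values affected by a listed condition, and show per-protocol completers as a sensitivity analysis.

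The cost is wording in three sections, one eCRF flag and one additional analysis. The downside is that some T2 values will be affected by the local condition or missing for safety, and a subject who had a premature-end visit may also attend T2. The flag and the completer analysis show how far affected values change the result.

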11.2. Procedure

All breaks in a volunteer's participation in the trial have to be recorded in the study termination form the reasons for discontinuation being mentioned. In case of volunteers did not perform the expected visit, the Investigator has to try to understand the reason of the absence.

11.3. Restrictions

The volunteers, who stop the trial, cannot be enrolled again or be replaced by other volunteers with the same randomization number.

12. STATISTICAL ANALYSIS PLAN

12.1. Main criteria

The statistical evaluations of clinical and instrumental data (adjusted means and standard deviation) and relative graphs will be performed at the times required by the protocol. The values will be rounded off to the decimal in accordance to our internal procedures.

12.2. Population description

This sample includes all subjects that completed the study according to the protocol.

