10.2. Intermediate visit (T1 1 month after the 1st aesthetic procedure)

The visit includes:

- record of possible adverse events or intervened illness
- pregnancy test (only for women not in menopause)
- clinical and instrumental assessments
- photographic documentation
- 2nd injection procedure.

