12.5. Statistical plan

The activity of the test product at each study time will be expressed in absolute values versus baseline (T0).

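### Section 12.2 restricts the analysis to protocol completers, which discards observed T1 changes and planned premature-end data and can bias a single-arm effect estimate, modestly and in an uncertain direction

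*Combined protocol and SAP*

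**What the plan says.** Section 12.2 describes one population: "This sample includes all subjects that completed the study according to the protocol". Sections 12.1 to 12.5 define no all-treated or safety set and no rule for missing values. Section 12.1 names the data to be evaluated ("The statistical evaluations of clinical and instrumental data (adjusted means and standard deviation"), and section 12.5 sets the contrast: "The activity of the test product at each study time will be expressed in absolute values versus baseline (T0". The study times after baseline are T1 (one month) and T2 (four months).

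Several routes out of the study can be linked to the product or procedure:

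- Section 9.2.3 (Adverse event follow up): "If the study product causes an adverse event, the Investigator could withdraw the subject from the study".
- Section 11.1 lists as withdrawal criteria a subject who "does not comply with the treatment" and one who "develops any of the conditions specified in the original exclusion criteria".
- Section 5.4 counts among those conditions a significant skin disorder on the test area, with local infection as an example.

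The protocol does plan to collect data from those who leave. Section 9.2.3 (AEs/Incidents reporting procedure) asks that they be encouraged to attend the final visit. Section 10.4 makes the premature-end visit the same as the final visit. Section 11.2 has the reasons recorded. Section 12 does not say how any of these data are analysed.

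Section 1 makes performance and tolerance together the primary endpoint. Section 9.1 lists what tolerance covers but gives no denominator.

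**The concern.** The 12.2 sample is chosen by what happens after treatment, and some of that can be a consequence of treatment. In an open, single-arm study no second arm shares the selection, so any distortion goes straight into the reported change from T0.

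The clearest case is T1. A subject who is treated, assessed at T1 and leaves before T2 has a complete T0-to-T1 change. Nothing is missing at T1, yet the subject is outside the 12.2 sample. Similarly, a subject who attends T2 after departing from the treatment plan has an observed T2 value that the rule can remove. Section 12 does not say which departures have that effect.

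What is at stake is the size of the reported effect. If leavers responded less than stayers, the completer figure favours the product. If they responded more, it does the opposite.

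**Working it through.** **Inputs.** Section 5.2 gives 55 enrolled to obtain at least 50 evaluable. The margin is 55 − 50 = 5, and 5/55 = 9.1%. The documents state no dropout rate, expected effect or standard deviation, so 50 and 55 cannot be derived independently. The loss counts and leavers' responses below are assumptions, shown as a range.

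**Effect on the mean change.** Let k of 55 treated subjects be lost, and let their mean change be f times the completers' mean change m.

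- All-treated mean = m × [(55 − k) + k·f] / 55
- Relative error of the completer mean = 55 / [(55 − k) + k·f] − 1

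| Leavers' change (f) | k = 1 | k = 3 | k = 5 |
|---|---|---|---|
| None (0) | 55/54 − 1 = +1.9% | 55/52 − 1 = +5.8% | 55/50 − 1 = +10.0% |
| Half (0.5) | 55/54.5 − 1 = +0.9% | 55/53.5 − 1 = +2.8% | 55/52.5 − 1 = +4.8% |
| Same (1) | 0% | 0% | 0% |
| 1.5 times | 55/55.5 − 1 = −0.9% | 55/56.5 − 1 = −2.7% | 55/57.5 − 1 = −4.3% |

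The same table applies at T1 to subjects who leave between T1 and T2. There the all-treated mean is observed, so the error can be avoided without any assumption about missing values.

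**Effect on the test.** Simulated changes (normal, SD 1, 50 completers, 20,000 runs) were analysed by paired t, then again with five zero changes added.

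| Completers' mean change | Mean t, completers | Mean t, five zeros added |
|---|---|---|
| 0.5 SD | 3.59 | 3.54 |
| 1 SD | 7.20 | 6.85 |

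The test statistic barely moves.

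**Two checks that shape the fix.**

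- Adding five zeros raises the Shapiro-Wilk rejection rate at 5% from 5.3% to 9.9% (mean 0.5 SD) and from 4.8% to 12.6% (mean 1 SD; 5,000 runs). Under section 12.4 this could switch the test between analyses.
- The usual Wilcoxon signed-rank test drops zero differences, so five added zeros leave its statistic and p-value unchanged. For the clinical score, a no-change analysis would then alter the mean but not the test.

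**The case against.** The strongest reply is about weight. The 10.0% figure needs all five spare subjects lost and none of them improved. With one loss the overstatement is at most 1.9%. Nothing in the documents shows that leavers respond less. Section 3 reports no injection-site or allergic reactions in preceding trials, withdrawal for a product-caused event is optional, and no injection follows T1, so an event after T1 cannot cost a subject a treatment. There is no randomised comparison to protect, and an analysis of evaluable cases with recorded withdrawals is a recognisable design. All of this stands, and it limits the size of the point. It does not explain why T1 changes already measured, or premature-end data already planned, should be left out.

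The scope of 12.2 is also inferred, since its opening words refer back to nothing specific. The inference is reasonable: it is the only population statement and it sits within the statistical plan.

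Sections 12.3 and 12.4 name no specific test. A method that needs complete cases, such as Friedman or repeated-measures ANOVA, could not use every T1 value. The fix must therefore name a per-visit paired comparison.

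A reader might infer that tolerance too is restricted to completers, so that reactions in subjects who leave would vanish from the reported rate. The documents do not support this. Section 9.1 takes in any adverse event during the study, and section 9.2.3 requires each to be documented and followed, which reads naturally as covering everyone treated. Section 12 gives no tolerance analysis at all, so the denominator is unstated and not limited by 12.2.

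**Conclusion.** The point holds for performance. On its natural reading, section 12.2 selects subjects on events that can depend on treatment and discards observed or planned data, while section 12.5 asks for change from T0 at every study time.

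Under assumed losses of 1 to 5 of 55, and leavers' change between none and 1.5 times that of completers, the error runs from −4.3% to +10.0% of the effect. The bias is modest and its sign is not known in advance. A reader might infer that the rule is bound to flatter the product or to create a significant result; neither follows from these figures. Significance would rarely change, but the reported effect size, which is the whole performance result here, can.

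For tolerance the finding is only that the denominator is not written down. The appendices were not available for this check.

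This should be corrected before data review; it does not undermine the study.

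**What to change.** Reword section 12.2 as follows:

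1. **Main performance analysis.** All subjects who received at least one injection and have a T0 value and a value at the visit analysed. Use a paired within-subject comparison at each visit: Wilcoxon signed-rank for the clinical score (12.3), and paired t or signed-rank for instrumental data by the rule in 12.4. T1 then uses every observed T1 value. T2 uses every observed T2 value, whether or not the subject complied fully.
2. **Sensitivity analysis with premature-end values.** Do not pool these values with T2 in the main estimate, because follow-up time and number of injections differ. List them with both, and include them in this one analysis.
3. **No-change sensitivity analysis.** Report the mean change with zero assigned to treated subjects who lack a T2 value, as a check on effect size. If a test is given, use the same one as in the main analysis and retain zero differences (for example, Pratt handling for the signed-rank test).
4. **Supporting analysis.** Keep the completers-per-protocol analysis, with the deviations that exclude a subject listed before data review.
5. **Clarification.** State that tolerance is reported over all subjects who received at least one injection.

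Item 1 removes the T1 problem for subjects who leave after T1. At T2 values may still be missing for reasons linked to response; items 2 and 3 show how far that could matter.

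The cost is SAP wording and one or two extra analysis runs on data already planned, with no new visits. Estimates may look slightly less favourable. The withdrawal criteria are unchanged.

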12.3. Clinical data

The statistical analysis of clinical data is carried out with not parametric test.

12.4. Instrumental data

The analysis of all numeric parameters (arithmetic mean, standard deviation) and their relative graphs are carried out:

- by non parametric test when the normality hypothesis is rejected by the Shapiro-Wilk test at the threshold inferior to 5%.

- by parametric test, when the normality hypothesis is confirmed by Shapiro-Wilk test.

